Randomization. Subjects who meet all inclusion/exclusion criteria will be randomly assigned by computer program (R-track®) using a minimization algorithm with equal allocation to one of two treatment groups: 1) active CPAP set at a level of pressure that will abolish nocturnal respiratory disturbances, or 2) sham-CPAP (placebo) where the level of pressure will not abolish nocturnal respiratory disturbances. Use of a minimization algorithm will insure treatment balance on three factors: 1) the participant's baseline physical activity levels in terms of mean number of steps per day based on the SenseWear Armband® ( $< 5,000, \geq 5000$ ), 2) whether the subject had previous diabetes education, and 3) whether the subject is prescribed insulin. Minimization is a form of adaptive treatment allocation in which the probability of assignment to the treatment groups does not remain constant, but is determined by the current balance and/or composition of the groups. Treatment group assignment will be generated and stored in a secured database. Subjects and all research team personnel involved in further data collection will be blinded as to which group the subjects are assigned. The University of Pittsburgh site will randomize participants from all the recruitment sites (West Virginia University, VAPSHS, University of Pittsburgh).

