**Preliminary Analyses.** Detailed exploratory data analyses will first be performed, involving data description and data screening for anomalies (e.g., outliers, nonnormality, etc.). The results from this initial investigation will be used to: 1) describe univariate and bivariate data distributions; 2) identify imbalances between treatment groups and associations between the dependent variables and suspected covariates/confounders); 3) evaluate the amount and patterns of missing data; and 4) check for the violation of statistical assumptions for the planned analyses. Covariates/confounders will be included in models secondarily and their effect on the results of primary predictors/factors will be evaluated. The randomness of missing data will be investigated using available information on subject characteristics to help discern patterns in the missing data, identify the possible covert missing data mechanisms, and inform the choice of the strategies to handle missing data. It is anticipated that the primary reason for data to be missing will be subject attrition. We will closely monitor attrition and conduct logistic regression models via SAS PROC LOGISTIC to compare the characteristics of participants who remained in the study versus those who dropped out to determine if data are missing at random. If the data are missing at random (i.e., not related to the outcome itself), likelihood estimation procedures, such as those used in SAS PROC MIXED, GLIMMIX and NLMIXED as well as Mplus, will produce unbiased estimates while allowing us to retain cases with missing values on the outcome variables. If needed, multiple imputation would be used to impute missing values on the predictor variables. If the data are not ignorably missing, we use pattern mixture or selection modeling to examine data attrition.

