Data Analysis Plan for Primary Aim 1. An "intent-to-treat" (ITT) approach will initially be used during data analysis when investigating efficacy of CPAP+DEC compared to sham-CPAP+DEC. All subjects will be included in the data analysis in the groups to which they were randomly assigned, regardless of the adherence to protocol, treatment received, withdrawal or deviation from protocol. Adherence with the assigned protocol, will be monitored throughout the duration of the study. With this ancillary information, the sensitivity of the results under the ITT model will be explored to identify the effects of the amount of intervention received and the deviations in protocol on the efficacy of the interventions. Since the primary endpoint of interest, glycemic control, is assessed repeatedly using two measures, fructosamine and A1C, linear mixed modeling (LMM) with linear contrasts to test the stated hypotheses. A flexible modeling approach, mixed modeling allows for unequally spaced assessments, fixed and time-varying covariates, dependent variables with data that are missing at random, and modeling the covariance/correlation among longitudinal responses. We will consider the baseline value both as an assessment point as well as a possible covariate in analyses. The primary independent variable is the randomized assignment to treatment (CPAP+DEC vs. sham-CPAP+DEC). Fixed and/or time-dependent covariates (including baseline outcome values) may be included in the repeated measures model as indicated secondarily based on the results on the preliminary data analysis to adjust for group imbalances or variables related to the dependent variable. Prior to fitting the repeated measures model, the structure of the estimated covariance matrix for the repeated measures will be carefully examined to determine the appropriate covariance structure. Fit indices will also be used to evaluate the repeated measures models estimated assuming different covariance structures to identify the most appropriate covariance structure. When fitting models, time will be treated as a fixed, repeated within-subjects factor, while treatment assignment will be a fixed, between-subjects factor, with an interaction between time and group. F-tests will be used to test the main and interaction effects included in the model. Individual regression parameters will be computed and reported with their asymptotic standard errors to yield confidence intervals. Sensitivity analyses will be performed to discern the impact of influential cases on results. To test the associated hypothesis (H1), linear contrasts will be specified and estimated when fitting the repeated measures model to compare, relative to baseline values, the CPAP+DEC and sham-CPAP+DEC groups on: 1) the 6-week values of fructosamine and A1C and the 2) 12-week values of fructosamine and A1C. Wald t-statistics will be used to test each linear contrast. Confidence intervals will be obtained for these linear contrasts. Marginal modeling with generalized estimating equations will also be used as it tends to be more robust to misspecification of the covariance structure of repeated assessments and violations in the normality assumption for continuous outcomes.

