
Analysis Strategy for Aim 2. Using the approach described for Aim 1, repeated measures models will be fitted, and linear contrasts will be estimated to compare 6-week and 12-week values for improvements in diabetes self-management outcomes (retention of information taught during the DEC classes [DKT], improved self-management behaviors [SDSCA], increased physical activity [SenseWare Armband steps], and decreased diabetes-related distress [PAID]) relative to baseline values between subjects on CPAP+DEC and those receiving sham-CPAP+DEC. Generalized linear mixed modeling or nonlinear mixed modeling will be used to analyze longitudinal categorical outcomes should outcome variables need to be categorized for analysis. Along with test statistics and p-values, point and interval estimates will be obtained for linear contrasts.

Analysis Strategy for Aim 3. We will *explore* adherence to CPAP (dose) and specific neuro-behavioral and physiological mechanisms (nighttime sleep, daytime sleepiness, mood, and vigilance during DEC sessions) as possible intervening, or mediator, variables that may mediate the effects of CPAP treatment on glycemic control and diabetes self-management outcomes. Initially, we will fit simple mediational models (predictor, single mediator, single outcome) and estimate whether the effects of CPAP (predictor) on changes in glycemic control and diabetes self-management outcomes are mediated through changes in specific neuro-behavioral and physiological variables (i.e., nighttime sleep, daytime sleepiness, mood, and vigilance during DEC sessions). Standardized parameter estimates of path linkages (with confidence intervals) will be obtained to summarize associations between the exogenous treatment variables, suspected mediators, and distal outcomes, as well as the indirect effect of the treatment group on the targeted outcomes through the suspected mediators and the direct effect of the treatment group on the outcomes. The goodness-of-fit of a model will be assessed using standard summary indices (e.g., RMSEA, CFI) as well as through residual analyses. Depending on the results for testing of individual mediators, we may combine the mediators into a multiple mediator model to develop a more complete picture of these hypothesized mechanisms of action for CPAP.

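### Making baseline and the minimisation factors fixed terms of the primary model would add precision at almost no cost

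*Combined protocol and SAP*

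**What the plan says.** The plan for Aim 1 (section C, Data Analysis Plan for Primary Aim 1) describes a linear mixed model in which time is a within-subjects factor and "treatment assignment will be a fixed, between-subjects factor, with an interaction between time and group". For H1, "linear contrasts will be specified and estimated when fitting the repeated measures model to compare, relative to baseline values", the two groups at 6 and at 12 weeks. The plan says that baseline will be considered both as an assessment point and as a possible covariate, and then that "Fixed and/or time-dependent covariates (including baseline outcome values) may be included in the repeated measures model as indicated secondarily", depending on the preliminary data analysis. The Preliminary Analyses paragraph agrees: "Covariates/confounders will be included in models secondarily". A second method is added without a stated rank: "Marginal modeling with generalized estimating equations will also be used".

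Aim 2 inherits all of this: "Using the approach described for Aim 1, repeated measures models will be fitted".

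Under Procedures, Randomization, "Use of a minimization algorithm will insure treatment balance on three factors": baseline steps below 5,000 or not, previous diabetes education, and prescribed insulin. Section C does not name these three as model terms. The Sample Size Justification works with mean changes from baseline and takes no credit for covariates.

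**The concern.** A mixed model with separate baseline means for each group does not by itself use the fact that randomisation makes those means equal in expectation. With complete data its contrast is the raw difference in mean change. Using that fact costs no patients and no new data.

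Three things are at stake. Aim 2 sets the trial size and has almost no spare power at its planning effect. A1C is the only Aim 1 measure planned at every site, because fructosamine is not done at WVU, and the sample size section gives no effect size for A1C. Finally, as long as covariates are chosen after looking at the data, the primary estimate is not fully fixed in advance.

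**Working it through.** **Inputs from the protocol.** Two-sided alpha .01, power .80, d = 0.53 in SDs of change, 84 completers and 105 enrolled per group, 20% attrition (Sample Size Justification). SDSCA test-retest mean of 0.40 (Study Measures, Aim 2).

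**Assumptions.** The documents give no baseline-to-follow-up correlation ρ for A1C or fructosamine, so ρ runs from .3 to .9. Baseline and follow-up SDs are equal until step 4. Missing follow-up is ignorable. One follow-up visit is considered at a time.

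**1. The plan's figure.** n = 2(2.576 + 0.842)²/0.53² = 83.2, so 84 per group; 168/0.8 = 210. This reproduces. With the noncentral t distribution, power at 84 per group is .795.

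**2. Variance of the group contrast** (SD set to 1, so the effect is 0.53 × √(2(1−ρ))):
- Raw change score, completers only: V0 = 4(1−ρ)/84.
- Planned likelihood model, 105 baselines and 84 follow-ups: V1 = 2[(1−ρ²)/84 + (1−ρ)²/105].
- Baseline means constrained equal: V2 = 2(1−ρ²)/84.

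Hence V2/V0 = (1+ρ)/2. Against the plan's own model, V2/V1 = (1+ρ)/(1.8+0.2ρ).

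Example at ρ = .5: V1 = 2(.75/84 + .25/105) = .0226 and V2 = .0179. The noncentrality is .53/√.0226 = 3.52 against .53/√.0179 = 3.97.

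**3. Power at d = 0.53, alpha .01** (noncentral t, 166 and 165 df)

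| ρ | V2/V1 | Planned model | Baseline-adjusted | 99% CI narrower by |
|---|---|---|---|---|
| .3 | .70 | .829 | .950 | 16% |
| .4 | .74 | .824 | .932 | 14% |
| .5 | .79 | .819 | .912 | 11% |
| .7 | .88 | .810 | .867 | 6% |
| .9 | .96 | .800 | .819 | 2% |

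The last column is 1 − √(V2/V1). The row for .4 matches the SDSCA test-retest figure.

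**4. Unequal SDs.** If the follow-up SD is k times the baseline SD, the complete-data ratio is k²(1−ρ²)/(1+k²−2ρk). At k = 1.1 (assumed) this is .82/.92/.97/1.00 at ρ = .5/.7/.8/.9. Entry limits of 6.5% and 11% on A1C truncate baseline but not follow-up, so k above 1 is plausible for A1C.

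**5. Cost.** If four added terms (baseline and three factors) predict nothing beyond the assumed ρ, chance imbalance inflates the variance by about 1 + 4/161 = 1.025. Adjusted power becomes .857 at ρ = .7 and .808 at ρ = .9. Break-even with the planned model solves 1.025(1+ρ) = 1.8 + 0.2ρ, so ρ is about .94. Minimisation limits imbalance on its own factors, so their share of this charge should be smaller.

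**6. Minimisation factors.** The documents do not say how strongly these predict change. In simulations with assumed strengths (168 subjects, ρ = .5 and .7, nominal alpha .01), leaving them out of the raw change contrast gave type I error of about .006 if they explain 10% of the variance in change, .004 if they explain 20%, and no material departure if they shift only the level. For the steps outcome, adding the step stratum to continuous baseline steps changed nothing (power .91 and .86 at ρ = .5 and .7 either way).

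**The case against.** The strongest reply is that nothing is broken. The test is valid, the sample size reproduces, and the plan expressly names baseline as a possible covariate. That stands. A reader might infer that the plan forbids or overlooks baseline adjustment; it does neither. What it does not do is make adjustment part of the primary test.

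The second reply is that the comparison should be with the plan's own likelihood model and not with a completers-only change score. That is also right. The planned model already keeps everyone with a baseline value and starts from .80 to .83, not from .795 throughout. The table uses that comparator.

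The third is that A1C may gain little. It reflects the past 2 to 3 months, so a 6-week value overlaps the baseline window, and recent medication changes are excluded. Both point to a high correlation, and the entry limits may make the SDs unequal. This stands: for A1C the gain could be close to nil.

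The fourth is that the strength of the minimisation factors is guesswork. It is. The case for including them is that the analysis should match the allocation; no figure in the documents supports a stated gain.

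**Conclusion.** The point holds as a free improvement. Against the plan's own model, baseline adjustment raises power at d = 0.53 by about 12, 9, 6 and 2 percentage points at ρ = .3, .5, .7 and .9. At the SDSCA value of .40 it goes from about .82 to .93. These figures rest on equal SDs, the planned 105 and 84 per group, and ignorable missingness.

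Three stronger readings are not supported:
- **That the planned test is biased or anti-conservative.** It is not. Leaving out balanced factors that predict change makes it conservative.
- **That the trial is underpowered for Aim 1.** No A1C effect is stated, so A1C power cannot be derived from the documents. Fructosamine power depends on how many participants are measured outside WVU, which is not given; at the plan's own 48 per group and d = 0.74 it is .838.
- **That adjustment always pays.** At very high correlation, or with a larger follow-up SD, the gain can vanish. The loss is then limited to the small cost in step 5.

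**What to change.** In the Aim 1 analysis, and by reference in Aim 2:

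1. Make the primary model a baseline-adjusted one. The preferred form keeps baseline in the response vector, constrains group means to be equal at baseline, and estimates the 6- and 12-week contrasts. It retains everyone with a baseline value, in line with the ITT statement.
2. Add prespecified factor-by-time terms for previous diabetes education, prescribed insulin and step stratum. For the steps outcome, continuous baseline steps replace the stratum.
3. Label the unconstrained change contrast, GEE and any model with data-selected covariates as sensitivity analyses.
4. State how the step factor is obtained at WVU. Randomization defines it from the armband, while Study Measures says that WVU uses a pedometer instead.

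The cost is SAP wording, one definition for WVU, and a few extra parameters per outcome against 168 planned completers. That is at most about 2.5% of variance if the four added terms predict nothing. No new data or patients are needed.

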**Aim 2 (Secondary):** To determine if CPAP + DEC is superior to sham-CPAP + DEC for improving diabetes self-management outcomes. **H2:** Subjects who receive CPAP + DEC will have better diabetes self-management outcomes (retention of information taught during the DEC classes, improved self-management behaviors, diabetes monitoring activities, increased physical activity, and decreased diabetes-related distress compared to subjects with sham-CPAP + DEC at 6 weeks and 12 weeks).

**Aim 3:** To explore adherence to CPAP (dose) and specific neuro-behavioral and physiological mechanisms (sleep quality, daytime sleepiness, mood, and vigilance that may mediate the effects of CPAP treatment on glycemic control and diabetes self-management outcomes (6 weeks and 12 weeks).

**Aim 4:** To explore the association between the durability of treatment of OSA (i.e. adherence to CPAP) and sleep quality, daytime sleepiness, mood, diabetes self-management, and glycemic control after 24 weeks of active CPAP in the full sample.

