Length of the intervention. The duration of the blinded intervention with sham comparison is 12 wks. This is based on previous studies in OSA patients demonstrating that improvements of objective sleepiness plateaus after 2 wks of treatment, results that are supported by several clinical trials that found significant improvement after 4 wks of CPAP treatment in subjective sleepiness, objective sleepiness, neuro-behavior outcomes, mood, and functional status. After the completion of the intervention, we will provide CPAP treatment to those subjects who were initially

randomized to sham-CPAP. We will follow all subjects for a total of 24 weeks of therapeutic CPAP treatment to evaluation durability of adherence to CPAP, glycemic control, and behavioral outcomes.

CPAP Titration Study/Sham-CPAP Titration. The nighttime CPAP titration PSG will be performed to determine the optimal level of CPAP needed to eliminate the subject's apnea. The CPAP titration PSG will be performed using standard techniques, with effective CPAP level defined as an AHI <5/hr with the minimum effective pressure for each subject. Patients randomized to the sham-CPAP arm will have titration studies that are performed identically to the CPAP titration except the standard CPAP connection will have a sham-CPAP restrictor piece added, the modified expiratory valve will be attached and pressure at the nose mask will be  $\leq 1$  cm H2O. The WhisperSwivel® connectors (sham and regular connectors) will be coded for the active CPAP intervention or the sham-CPAP group. A trained research Registered Polysomnographic Technologist at will choose the appropriate connector and record the number and the group (CPAP/sham-CPAP) in a secure file; this person is unblinded. The sham CPAP blower will be set at a pre-set level (this pressure is not transmitted to the subject, but determines the blower sound). The level of pressure for the blower of each sham CPAP participant will be displayed to participants as a "10 cm of H2O".

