**Assessment 3 with Unblinding/ Debriefing.** (week 12- of CPAP/sham-CPAP use). Subjects will be sent the questionnaires, the SenseWear Armband® to use for 7-days before returning for Assessment #3. Subjects will return to the study site with those items, their glucose meter and pedometer. In addition, they will bring their CPAP/sham-CPAP machines and masks. Anthropometric measurements and a venipuncture to obtain fructosamine, A1C, and lipid profile will be done. Prior to being informed of his/her treatment condition, the subjects will be asked to which arm of the study they think they were assigned. The Project Manager/ Study Coordinator and/or PI will debrief the subject, answer any questions and provide a copy of their sleep and laboratory data.

Crossover to Active CPAP. The crossover to active CPAP is important because of two reasons: 1) ethical considerations and 2) the pilot/feasibility study subjects identified the possibility of eventually being able to try CPAP treatment was a major reason they considered participating in the study. VAPHS subjects who were in either the active and sham-CPAP group will be directed to the Sleep Center at the VAPHS for follow-up care. Non-VAPHS subjects in the sham-CPAP group will be offered the chance to have an actual CPAP titration study, as described above, receive the CPAP education and monitoring, and start CPAP.

**Assessment 4.** (week 24) All subjects are reassessed as described above; it is the final assessment for those who were initially on active CPAP. We will provide those subjects with a summary of their sleep and laboratory data. Those subjects that crossed-over to active CPAP will continue.

**Assessment 5.** (wk 36) Those subjects who crossed-over to active CPAP will have their final assessment (after 24 wks of active CPAP) performed as described above. Subject will receive a final debriefing by the Project Manager /Study Coordinator and/or the PI and a copy of their sleep and laboratory data.

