**Change in protocol 7.12.2018 (all sites)**

- Assessment 4 will be the final assessment for both Active and Sham. Subjects originally on Sham will be offered 12 weeks of Active treatment, instead of 24 weeks of Active treatment
- Assessment 5 is removed from protocol

- **The maximum compensation for both Active and Sham is \$280**

**Data Management.** Data processing and management will be conducted in the Center for Research and Evaluation (CRE) at the University of Pittsburgh under the supervision of [name], Director of CRE and co-investigator for this project. The CRE also provides support for form design, data entry and verification, programming, and data management as fee-for-service. The CRE supports the design and implementation of paper-and-pencil, computer-based and web-based data collection forms.

The CRE will serve as the data processing center for all data collected. Form design and data management will be conducted in the CRE under the supervision of [name], Director of CRE and co-investigator/statistician for this project. Oracle (version 11g, Oracle Corp., Redwood Shores, CA) will be used for data management. Data will be collected in three forms: paper-and-pencil instruments, electronic monitors, and biological values. For paper-and-pencil instruments, Teleform Elite (version 10, Verity, Inc., Sunnyvale, CA), a Windows-based software package for automated data entry/verification, will be used for form design, data entry, and data verification.

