Analysis Strategy for Aim 4. For this aim we will combine the 6 months of data for the two groups receiving CPAP (including the participants in the delayed treatment group who crossover to CPAP) to *explore* retention of treatment effects and to explore the association between the durability of treatment of OSA (i.e. adherence to CPAP) and 1) sleep

quality [PSQI], 2) daytime sleepiness [ESS], 3) mood [POMS], 4) diabetes self-management [SDSA, DES-SF, PAID7, and 5) glycemic control [fructosamine and A1C] after 24 weeks of active CPAP. For delayed treatment group participants, the initial assessment for this analysis will be their assessments at 12 weeks from study start. Random coefficient modeling will be applied to model changes in sleep quality, daytime sleepiness, mood, diabetes self-management and glycemic control and to associate these changes with objectively measured CPAP adherence via the EncoreAnywhereTM. Estimated regression coefficients and confidence intervals will be reported to summarize changes in outcomes over time and their associations with CPAP adherence.

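### Aim 4 still promises 24 weeks of active CPAP in the full sample, but after the 7.12.2018 change the last visit of sham-first subjects falls at nominally 12 weeks on CPAP

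*Combined protocol and SAP*

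**What the plan says.** **Aim and analysis.** Section A (Aim 4) sets the horizon as "after 24 weeks of active CPAP in the full sample". Section B (Design) likewise plans to pool six months of data after the crossover. Section C (Analysis Strategy for Aim 4) combines six months on CPAP from both groups, ending with "glycemic control [fructosamine and A1C] after 24 weeks of active CPAP". For the delayed-treatment group it fixes time zero: "the initial assessment for this analysis will be their assessments at 12 weeks from study start". The model is a random coefficient model of change over time, related to measured CPAP adherence. No arm term is named.

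**Schedule behind that text.** Length of the intervention: "We will follow all subjects for a total of 24 weeks of therapeutic CPAP treatment". Under Procedures, Assessment 4 is at week 24, and Assessment 5 at week 36 is for the crossover group: "Those subjects who crossed-over to active CPAP will have their final assessment (after 24 wks of active CPAP) performed as described above". Measures to Reduce Attrition and Research Study Compensation also still carry the 36-week course or the fifth assessment for the sham arm.

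**Schedule after the change.** The block dated 7.12.2018, for all sites, makes Assessment 4 final for both arms. It adds "Subjects originally on Sham will be offered 12 weeks of Active treatment, instead of 24 weeks of Active treatment" and "Assessment 5 is removed from protocol".

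**The concern.** The Aim 4 horizon and population fit only the schedule before the change. Under the current one, sham-first subjects have no visit between 12 and 24 weeks on CPAP. The gap follows the randomised arm by design, so it is not ordinary dropout. A single pooled trajectory would let CPAP-first subjects stand in for sham-first subjects over the second 12 weeks, and the result would be read as 24-week durability in everyone.

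The arms are also not interchangeable on the CPAP clock. In their first 12 weeks on CPAP, CPAP-first subjects are blinded and receive the diabetes education and counselling (DEC), which begins about a week after the device. Crossover subjects had DEC during the sham period and were told their assignment at Assessment 3. At stake is what Aim 4 can conclude about durability, which is its purpose.

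**Working it through.** **Inputs.** Visit weeks: Procedures and the 7.12.2018 block. Time zero for sham-first subjects, study week 12: Analysis Strategy for Aim 4. Numbers, 210 enrolled (105 per group) and 168 completers (84 per group): Sample Size Justification.

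**Step 1: the plan's own figure.** For sham-first subjects, weeks on CPAP = study week − 12. Before the change, weeks 12, 24 and 36 give 0, 12 and 24. The 24-week horizon is therefore reproduced, but only under that schedule.

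**Step 2: the current schedule.** Weeks 12 and 24 give 0 and 12. The 12 is nominal: crossover requires a fresh titration study and education before CPAP starts, so exposure at study week 24 may be shorter.

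| Group | Weeks on CPAP at visits | Sum of squares of time |
|---|---|---|
| CPAP-first | 0, 6, 12, 24 | 315 |
| Sham-first, before the change | 0, 12, 24 | 288 |
| Sham-first, after the change | 0, 12 | 72 |

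Each sum of squares is Σ(t − mean t)². For example, 0 and 12 have mean 6, so 36 + 36 = 72.

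**Step 3: subjects with a 24-week value.** If no sham-first subject had completed Assessment 5 before the change, only the CPAP-first arm contributes: at most 84 of 168, or 105 of 210. If all had, the figures stay at 168 or 210. The documents do not say where between these limits the trial lies. The 84 and 168 allow for attrition over 12 weeks only, so actual 24-week numbers may be lower.

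**Step 4: information on a pooled linear slope.** Assumptions: equal arms, full crossover, no earlier Assessment 5 completers and no between-subject slope variance. A subject's information is then proportional to the sum of squares. Per pair of subjects, one from each arm:

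- before: 315 + 288 = 603
- after: 315 + 72 = 387
- retained: 387/603 = 0.64
- standard error ratio: √(603/387) = 1.25

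The documents give no slope variance. With r the ratio of slope variance to residual variance (per week squared), a subject's information is proportional to 1/(r + 1/S), S being the sum of squares. For assumed r from 0.0005 to 0.02, retained information runs from 65% to 85%, so the standard error rises by about 24% down to 9% (√(1/0.652) = 1.24; √(1/0.847) = 1.09).

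**The case against.** **The dated block may be only a change log.** It is not. It sits in the protocol body and states the schedule that now applies at all sites. The text left behind is the current aim and its analysis.

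**Mixed models accept unequal follow-up.** They do, and Section C says so for Aim 1. The model can be fitted and all observed data can stay in it. But fitting does not create sham-first observations after 12 weeks. Without an arm term, that stretch is filled from the other arm or by extending a 0–12 week slope.

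**The CPAP-first arm is a randomised half of the sample.** Its 24-week result is therefore not distorted by selection into that arm. This stands: the loss is mainly one of precision and of whom the statement covers. The provision in Section C for adding covariates secondarily could also admit an arm term, though none is planned.

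**Stronger readings that a reader might infer, but that the documents do not support:**

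- *No sham-first subject has 24-week data.* Some may have completed Assessment 5 before July 2018; no count is given.
- *The standard error rises by 41%.* √(168/84) = 1.41 applies to a mean 24-week change with full crossover and no earlier completers. The Aim 4 analysis names modelled changes and adherence associations instead. Full crossover is not assured either: "Non-VAPHS subjects in the sham-CPAP group will be offered the chance to have an actual CPAP titration study", while VAPHS subjects in both arms are directed to their own sleep center.
- *Pooled analysis must stop at 12 weeks.* Cutting the CPAP-first arm to 0, 6 and 12 lowers its sum of squares from 315 to 72. Slope information per pair falls from 387 to 72 + 72 = 144, a further standard error factor of √(387/144) = 1.64 under the Step 4 assumptions. The inconsistency does not require that sacrifice.

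**Conclusion.** The point holds as a mismatch between the Aim 4 horizon and population and the operative visit schedule. Under the 7.12.2018 schedule, a 24-week durability result cannot be given for the full sample. It can be given for the CPAP-first arm, plus whatever sham-first subjects had already reached Assessment 5.

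The 64% and 25% figures are illustrative and depend on the assumptions of Step 4. Earlier completers or slope variance between subjects make the loss smaller. Partial crossover alters the baseline for comparison as well. The schedule arithmetic rests on none of these assumptions.

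Nothing here reaches Aims 1 and 2, whose contrasts end at 12 weeks, or the sample of 210. Aim 4 is exploratory, so this is a correction that should be made, not a flaw in the trial's main inference.

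**What to change.** Reconcile these places with the 7.12.2018 block: Aim 4 in Section A; Design; Length of the intervention; the crossover and assessment text under Procedures; Measures to Reduce Attrition; Analysis Strategy for Aim 4; and Research Study Compensation, including Table 6 and the payment schedule after it. This review takes no view on which treatment duration is right.

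If the change stands:

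1. Restate Aim 4 so that 24-week durability is reported for the CPAP-first arm. Count earlier Assessment 5 completers and show them separately. Do not present a pooled 24-week result as covering the full sample.
2. Keep all observed data in the random coefficient model, and add randomised arm and arm-by-time terms.
3. Report the 0–12 week change on CPAP by arm, noting the differences in DEC timing and blinding. Note too that sham-first exposure at the last visit may be under 12 weeks.
4. State that estimates beyond 12 weeks rest on the CPAP-first arm, apart from any earlier completers.

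The cost is wording in several sections and extra terms in one exploratory model, with no new data. The 24-week statement will rest on fewer subjects, and the arm terms cost a little precision.
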